## 8.6 SAFETY OVERSIGHT

Safety oversight will be under the direction of a DSMP composed of individuals with the appropriate expertise, including Neurology/Radiology. The DSMP members will only meet to discuss reported AEs. A written reported will be submitted to the DSMP group every 6 months. At this time, each data element that the DSMP group needs to assess will be clearly defined. The DSMP group will provide its input to the PI and IRB.

## 9 CLINICAL MONITORING

#### **Roles and Responsibilities**

The PI, [name], will be responsible for working with the IRB to ensure the participants' safety on a daily basis. In addition, we assembled independent safety monitors (ISM) as a part of our

DSMP to oversee trial safety, data management, analysis and guality assurance. [name]. (Assistant Professor, UT Southwestern Medical Center), [name]., Ph.D. (Assistant Professor, UT Southwestern Medical Center) and [name]. (Neurologist, Walter Reed National Military Medical Center) will oversee the study protocols, monitor the safety of the participants, and ensure data security. Drs. [name], [name], and [name] (outside member) are not associated with the trial and have no conflicts of interest with the study team or proposed institutions. [name] will be responsible for reviewing protocol adherence, quality control, regular data verification and protocol compliance. Over the last 4 years, [name] has assisted [name] on various pilot clinical studies at UT Southwestern Medical Center. His role of those studies was to examine computed tomography (CT) and magnetic resonance imaging (MRI) to screen for intracranial injuries within research subjects enrolled in [name] clinical studies. Drs. [name] and [name] will be responsible for monitoring data management, analysis and quality assurance by reviewing the data sources, the security measures in place to protect data sources (how data will be labelled and stored), and adherence to Good Clinical Practice and regulatory requirements. At UT Southwestern Medical Center, [name] has previously served on a number data safety monitoring boards.

The ISMs will meet with the investigative team at the start of the trial. The study coordinator will complete monthly reports detailing the study progress enrollment status, other medications taken by the participants during the trial (to screen for concomitant drug use), any adverse events (AEs), and any protocol deviations.

#### **Trial Safety**

Throughout the study, the study coordinator and investigators will monitor the participants for AEs. The study coordinator will contact the study participants every 7 days to monitor for adverse events. To monitor for drug toxicity, at the 2nd visit to UT Southwestern Medical Center (day 1-3), 8cc of blood will be collected to determine toxicology, liver function, and coagulation after taking the study drug (sildenafil) for 1-3 days. The study participants will be asked to notify the study team if planning to take any other drug besides the study drug. The participants will also be asked to maintain a daily log of medications taken other than the study drug to monitor drug to drug interactions.

Safety oversight will be under the direction of study PI, medical monitors (Drs. [name] and [name]) and the research coordinator. A written reported will be submitted to the DSMP members every 6 months. The ISMs will only meet to discuss reported AEs. Events determined by the PI and co-investigators to be unexpected adverse events involving risks to subjects or others will be reported by the contact PI to the IRB and FDA within 7 business days. With respect to unexpected adverse events, the contact PI will inform the ISMs within 24 hours of this occurrence and will provide the ISMs with AE listing reports. The ISMs will convene an ad hoc meeting by teleconference or in person as soon as possible and provide recommendations for proceeding with the study to the study sponsor and IRB. The ISM will provide its input in the report to the PI and IRB. The contact PI will inform the FDA if there is a temporary or permanent halt of the study. All study members will be informed by the contact PI about any unexpected adverse events.

Upon the reporting of unexpected adverse events a participant, the study coordinator will collect a blood sample (8cc) to determine blood chemistry and will conduct follow up medical monitoring. The Quest Diagnostics laboratory (Dallas, Texas) will perform the biochemical tests. The subject information, adverse event report (if any), and research chart will be kept in a locked file cabinet in the research office (South Campus H7.126). Only study investigators and coordinators will have access to the subject's file.

## 10 STATISTICAL CONSIDERATIONS

#### 10.1 STATISTICAL AND ANALYTICAL PLANS

#### STATISTICAL ANALYSIS PLAN

#### Study design and randomization scheme

Once eligibility is confirmed, based upon defined inclusion and exclusion criteria, randomization will occur within 2 hours of a bout. The placebo-controlled double-blind design will diminish concern about predictability of treatment assignments. The unblinded study biostatistician will prepare a randomization schedule. Randomization will be 1:1 sildenafil:placebo, and will be in blocks of 2. Treatment allocation will be determined via a computer program that automatically generates random digits. Investigators associated with this study will not have access to the randomization schedule. The randomization program will also record the assignments to the corresponding boxers in the database and will display the assignments on the screen for action by the study coordinators.

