## 4 STUDY DESIGN AND ENDPOINTS

#### 4.1 DESCRIPTION OF THE STUDY DESIGN

In this placebo-controlled, double-blinded clinical trial, approximately 100 boxers/MMA fighters that have experienced a concussion or a significant number of sub-concussive blows will be treated with a placebo pill or Viagra® (sildenafil; 60mg) once (single-dose therapy) or once-a-day for 14 days. This is a phase 2 study that will be conducted at a single-site (UTSWMC, Dallas, Texas).

Prior to competition, the medical/concussion history and a blood (8ml) and saliva sample will be collected at the baseline (pre-fight) visit. Also, a battery of neuropsychological exams (NIH Common Data Elements) and a magnetic resonance imaging (MRI) scan will be performed at UT Southwestern Medical Center Advanced Imaging Research Center to obtain cognitive, structural, and functional baseline data.

At day1-3 and 30 after injury, the boxers will undergo the MRI structural and MRI BOLD (with hypercapnia) procedures at UT Southwestern Medical Center Advanced Imaging Resource Center. The subjects will also undergo neurpsychological testing, and blood/saliva collection for tests to determine the efficacy of sildenafil. A randomization schedule will be prepared by the study statistician. Randomization will be 1:1 sildenafil:placebo, and will be in blocks of 2. Investigators associated with this study will not have access to the randomization schedule. The principal investigator, study team, and study subjects will be blinded in this study. To monitor the drug administration, a daily diary will be filled out by the participant. The tolerability of sildenafil in boxers will also be assessed.

A total of 130 boxers will be screened and only 100 boxers will be enrolled in this study to complete the study aims. The study participants will not be responsible for any research related costs, which include travel and parking when visiting UTSWMC for the collection of blood/saliva, neuropsychological testing, and MR imaging. The participants will be compensated for their time.

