The participants in **group 1** (single therapy) will consist of the active boxers/MMA fighters that experience significant sub-concussive blows or a concussion during competition. In this group, 65, professional male/female boxers/MMA fighters within the North Texas region will be screened and about 50 concussed athletes will be enrolled. The athletes that have at least 25 blows to the head and a Symptom Score > 1 on at least 3 items from the Rivermead Post-Concussion Questionnaire following their fight will be enrolled in this study. The research subjects will be treated with sildenafil (60mg), once at 2 hours after experiencing a concussion.

**Group 2** will consist of the active boxers/MMA fighters that experience significant subconcussive blows or a concussion during competition. In this group, 65, professional male/female boxers/MMA fighters within the North Texas region will be screened and about 50 concussed athletes will be enrolled. The athletes that have at least 25 blows to the head and a Symptom Score > 1 on at least 3 items from the Rivermead Post-Concussion Questionnaire following their fight will be enrolled in this study. Once enrolled, the subjects will be treated with sildenafil (60mg) once-a-day for 14 days.

**Healthy Control group:** In this study, 80, age (between 18 and 35)-matched healthy controls will be enrolled. The control subjects will participate in neuropsychological testing, blood/saliva collection, and the MR imaging procedures. Healthy controls will be tested in group 1 (n=40) and 2 (n=40) and randomized to receive either sildenafil or placebo in this group.

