#### 4.2.1.b. TBI Neuropsychological Assessments

In this clinical study, we test whether sildenafil improves cognitive, mood, and functional outcomes in injured boxers. The testing procedures will be conducted in a quiet room at UTSWMC by a neuropsychologist or trained coordinator. We anticipate that the testing procedures will take approximately 1 hour to complete. The subjects will be given frequent rests and they have the right to refuse to answer any questions or to stop a test at any time and for any reason. TBI phenotyping instruments recommended for evaluation in all TBI cohort or natural history studies have been labeled the TBI Common Data Elements (CDEs)(58). The subject will be interviewed, complete questionnaires, take pen-and-paper tests, and perform simple actions.

In this study we will include the following selected subset of assessments taken from the CDE's:

- Hopkins Verbal Learning Task (HVLT). The **Hopkins Verbal Learning Test** (HVLT) is a brief verbal learning and memory test with six alternate forms of 12 words.
- The Sport Concussion Assessment Tool (SCAT5), from the Concussion in Sport Group, is a standardized tool for evaluating injured athletes for concussion and can be used in athletes aged 13 years and older. This test will take approximately 30 minutes.
- Satisfaction with Life Scale (SWLS): is a short 5-item instrument designed to measure global cognitive judgments of satisfaction with one's life. The scale usually requires only about one minute of a respondent's time.
- Rivermead Post-Concussion Symptom Questionnaire: rate the severity of 16 different symptoms commonly found after a TBI (5 min).
- Galveston Orientation and Amnesia Test (GOAT)-modified for sports athletes

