#### **Stopping rules**

We do not anticipate a stopping rule for efficacy as the primary and secondary endpoints of the proposed study are clinically important, but intermediate. Even if we cannot reject the null hypothesis for the primary end point, we have multiple secondary endpoints that could still benefit our understanding towards the effect of sildenafil on concussed injury. Data collected in this study will be used to conduct a power analysis to design and implement the definitive study.

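### Fixed, published blocks of 2 let one known assignment reveal its pair-mate, the blind relied on is not secured for coordinators, and no method of assigning regimen is stated

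*Combined protocol and SAP*

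**What the plan says.** Section 4.1 and the SAP (section 10.1, Study design and randomization scheme) carry the same sentence: "Randomization will be 1:1 sildenafil:placebo, and will be in blocks of 2". The trial has one site.

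The SAP names one safeguard against guessing: "The placebo-controlled double-blind design will diminish concern about predictability of treatment assignments". Section 4.1 adds: "The principal investigator, study team, and study subjects will be blinded in this study", and section 10.2.1 repeats this. The SAP also says: "Investigators associated with this study will not have access to the randomization schedule". The same SAP paragraph then says that the randomisation program "will display the assignments on the screen for action by the study coordinators", and section 6.2 has the study coordinator work from the schedule and hand over the bottles.

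On regimen, section 4.1 describes Group 1 (single dose) and Group 2 (daily for 14 days) with the same entry criteria. For each it says: "65, professional male/female boxers/MMA fighters within the North Texas region will be screened and about 50 concussed athletes will be enrolled". It gives no rule for which athlete joins which group. Section 10.2.1 says that athletes are randomised 1:1 to placebo or sildenafil for single or multiple doses, which can be read as covering regimen or as covering drug only. The power section assumes 50 concussed boxers in each arm.

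**The concern.** Two is the smallest possible block for a 1:1 trial, and everyone who reads the protocol knows the size. Any event that reveals one participant's arm, whether a display, a deliberate unblinding or a telling side effect, therefore also reveals the pair-mate's arm, with the same degree of certainty.

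Two things are at stake. The first is selection after the bout: the eligibility wording leaves some room for judgement, since section 4.1 joins the blow count and the symptom threshold with *and*, while sections 7.3.1 and 10.2.1 join them with *or*. The second is assessment. Symptoms and cognition are among the primary endpoints, and section 4.2.1.b says: "The testing procedures will be conducted in a quiet room at UTSWMC by a neuropsychologist or trained coordinator".

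The missing regimen rule is a separate gap. Without a stated method, separate lists or stratification, a reader cannot tell whether drug and placebo are balanced within each regimen. Nor can a reader tell whether any contrast between regimens would be protected by randomisation.

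**Working it through.** The documents give no predictability figure to reproduce, so the steps below build one.

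**1. Blocks, with earlier assignments known.** Enumerate all permuted blocks of size 2h at 1:1. An assignment is determined when one arm has no places left. The share determined comes out as 1/(h+1). The best guess is the arm with more places left.

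| Block size | Determined | Best guess correct |
|---|---|---|
| 2 | 1/2 = 50% | (50% + 100%)/2 = 75% |
| 4 | 1/3 = 33% | 71% |
| 6 | 1/4 = 25% | 68% |
| 8 | 1/5 = 20% | 67% |

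For 100 athletes in blocks of 2, that is 50 assignments. The rows for 4 to 8 assume that the size is known; hiding and varying it would lower them further.

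**2. Blocks of 2, with the first assignment only guessed.** At 1:1, P(sildenafil | event) = s/(s+p), where s and p are the event rates on sildenafil and placebo. In a pair, the other member is on placebo with that same probability.

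- Flushing, Table 4 (10% v 1%): 0.10/0.11 = 91%. Table 7 (9-15% v 4%): 0.09/0.13 = 69% to 0.15/0.19 = 79%.
- Headache, Table 4 (16% v 4%): 0.16/0.20 = 80%. Table 7 (42-49% v 39%): 0.42/0.81 = 52% to 0.49/0.88 = 56%.

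Table 7 is for dosing three times a day and its population includes hospitalisation for pulmonary arterial hypertension, so neither table matches this trial. The two serve as a range.

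**3. How often a cue appears** (assuming that headache and flushing are independent).

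- Table 4: sildenafil 1 − 0.84 × 0.90 = 24.4%; placebo 1 − 0.96 × 0.99 = 5.0%; average about 15%. So about 85% show neither.
- Table 7: placebo 1 − 0.61 × 0.96 = 41.4%; sildenafil from 1 − 0.58 × 0.91 = 47.2% (40 mg) to 1 − 0.51 × 0.85 = 56.7% (80 mg); averages 44% to 49%. So 51-56% show neither, and the commoner cue, headache, says almost nothing.

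Guessing sildenafil when either cue appears and placebo otherwise is right in ½(0.244 + 0.950) = 60% of cases on Table 4, and in ½(0.472 + 0.586) = 53% to ½(0.567 + 0.586) = 58% on Table 7. No information gives 50%.

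**4. The blind, text against text.** Sections 4.1 and 10.2.1 call the study team blinded. The SAP displays assignments to coordinators without saying whether as an arm or as a code, and section 6.2 has the coordinator follow the schedule. The coordinator role also identifies eligible athletes (7.3.1, shared with a boxing consultant), contacts participants every 7 days about adverse events (section 9) and may give the cognitive tests (4.2.1.b). I assume that these are the same role or overlap; the text does not separate them.

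**5. Regimen and arm size.** 100 athletes / 2 regimens / 2 arms = 25 per arm within a regimen. Even the 110-120 athletes in section 10.2.1 give only 27.5-30. So 50 per arm is reached only by pooling the regimens. Neither separate lists nor stratification by regimen is stated.

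**The case against.** The strongest reply is that a block size is harmless while the blind holds, and the plan specifies a double blind, a placebo of similar appearance and no investigator access to the schedule. That is largely right. A reader might infer that every second assignment can be deduced; the documents do not support this. It is true only if the first of the pair is unmasked. From side effects alone, guessing is right about 53-60% of the time, and headache is a poor cue in athletes enrolled after blows to the head. Consent comes before the bout, a knockout is scored by the referee, and CBF/CVR is measured by MRI, so those parts are less exposed than symptoms and cognition. What remains is that the blind is left open at the coordinator, where the roles meet.

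A reader might also infer that athletes reach their regimen by no random process. The text is silent in section 4.1 and ambiguous in section 10.2.1, and the design schematic is not available here. The supportable statement is that no method is stated.

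A third tempting reading is that the trial sets out to compare regimens and cannot do so fairly. Sections 4.2.1 and 10.1 hypothesise that both regimens work, and no single-dose versus 14-day test is written. The SAP looks ahead only this far: "Data collected in this study will be used to conduct a power analysis to design and implement the definitive study". That does not speak of choosing a regimen. Sildenafil versus placebo remains randomised.

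**Conclusion.** The point stands in a bounded form and is worth an amendment.

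- **Blocks.** Fixed, published blocks of 2 at one site make 50% of assignments certain once earlier ones are known, against 33% for blocks of 4 and 25% for blocks of 6. This figure assumes a leak. If coordinators see codes only and the blind holds, the exposure is the much smaller one in steps 2 and 3.
- **Blind.** The sections on the coordinator's access and on the blinded study team do not fit together as written. Whether the display shows the arm is unknown, and it decides which of the two exposures applies.
- **Regimen.** No assignment method or stratification is stated, while the power assumption needs the two groups pooled if 100 athletes are enrolled. The drug-placebo comparison is not invalidated. Any contrast between regimens would have no stated protection from randomisation.

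**What to change.** 1. Replace blocks of 2 with permuted blocks whose size varies at random. Generate them separately within each regimen group (for example 4 and 6), and disclose the sizes neither in the protocol nor to site staff. Use a separate list of the same form for the healthy controls.
2. State how regimen is assigned. Either randomise it, 1:1:1:1 across the four combinations, or keep separate lists, include regimen group in any pooled analysis and declare that no single-dose versus 14-day comparison will be made.
3. If regimen is randomised, use blocks of 8 and 12. Regimen is visible from the number of pills, so a four-arm block of 4 holds one sildenafil and one placebo per regimen and is still a block of 2 within it; blocks of 8 and 12 act as 4 and 6.
4. Have the program show coordinators only coded bottle numbers, and reconcile sections 6.2 and 10.1 with the blinding statements in sections 4.1 and 10.2.1. Settle at the same time who holds the list: sections 4.1, 10.1 and 10.2.1 give it to the statistician, sections 6.1.1 and 6.2 to the pharmacy.

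The cost is a new list, an amendment and slightly looser running balance between arms. No extra participants are needed. It should be done before the list is used, because analysis cannot restore lost concealment.

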#### Outcomes

**Primary endpoints-** The absolute changes in global and regional CBF/CVR to hypercapnia and improved symptoms and cognitive performance.

Secondary endpoints- Effect of sildenafil on brain biomarkers in blood after injury.

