	matter degeneration (3-13). Recently, use of magnetic resonance imaging (MRI)-Blood Oxygen Level Dependent (BOLD) combined with hypercapnia (high spatial and temporal resolution) by our research group has proven to be more sensitive at measuring alterations of cerebral blood flow (CBF) in TBI subjects. The goal of our proposed research is to test the efficacy of Viagra® (sildenafil) at normalizing CBF and improving cognitive outcomes in people that have experienced a TBI. Sildenafil is a phosphodiesterase-5 (PDE- 5) inhibitor that has previously been administered as a therapy for high blood pressure and erectile dysfunction (14, 15). In people that have been affected by stroke-induce neurotrauma, sildenafil improved CBF and was found to be neuroprotective (16-21). With respect to chronic TBI, our preliminary data demonstrates that sildenafil therapy potentiates cardiovascular reactivity (CVR) in areas of the brain with damaged endothelium. In this proposal, we will test the hypothesis that sildenafil treatment in boxers/MMA fighters soon after concussion normalizes CBF, potentiates CVR, reduces post-concussion symptoms, and improves cognition.
Objectives:	
 
Objective 1: To demonstrate that administration of the vasodilator, sildenafil, to concussed boxers/MMA fighters will improve/normalize various vascular properties.
 
Objective 2: We will determine if sildenafil reduces symptoms and improves cognition in the athletes.
 

Endpoint	The primary outcome measures will be global CVR to hypercapnia, reduced symptoms, improved cognition in concussed athletes treated with a single or multiple doses of sildenafil (60mg). In the secondary outcome measure, we assess sildenafil (60mg) therapy reduces the levels of fluid-based biomarkers of injury.
Population:	The study population for this protocol consists of 100 boxers between the ages of 18 and 35 (both men and women) who have suffered a concussion. The athletes will be recruited from fitness centers within the North Texas area. Testing will occur at UT Southwestern Medical Center, Dallas, Texas. The study will be comprised of the experimental (boxers/MMA fighters) and age- matched non-boxer, healthy controls.
Phase:	2
Number of Sites enrolling participants:	1

STU032018-063, [name], FormA-ResearchProtocol, Mod\_6, 11-25-19 (1) NIH-FDA Clinical Trial Protocol

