## 4.2 STUDY ENDPOINTS

## 4.2.1 PRIMARY ENDPOINT:

To determine if sildenafil administration improves CBF/CVR, reduces symptoms, and improves cognitive performance in concussed boxers/MMA fighters. Hypothesis: Both single and multiple sildenafil therapy improves CBF/CVR, symptoms, and cognition in concussed boxers. Also, long-term administration of daily doses of sildenafil to concussed boxers/MMA fighters is well tolerated. Following injury, we will enroll 100, active boxers/MMA fighters and 80, controls into a double-blind, placebo-controlled study. At a 1:1 ratio, the subjects will receive a single treatment of either placebo or sildenafil. The purpose of this study is to determine if sildenafil treatment improves CBF/CVR, reduces symptoms, and improves cognitive outcomes. In this study we will treat the injured athletes once (within 2 hours of injury) or daily (for 14 days) to determine if sildenafil improves outcomes. Previous clinical studies conducted by our research group, we found that sildenafil treatment (60mg) is tolerable within the TBI population. The athletes will maintain a daily diary of symptoms. At day 1-3 and 30 after injury, the CBF/CVR MR imaging procedures, the Rivermead Post Concussion Symptom Questionnaire, and neuropsychological assessments (NIH Common Data Elements) will be conducted to study the effect of sildenafil therapy. Blood (8cc) and saliva will also be collected to measure brain biomarkers of injury. Tolerability (blood testing and symptom reporting) assessments will be conducted throughout the study to ensure that the symptomatic boxers tolerate multiple, daily doses of sildenafil.

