Also, we will assess the treatment effect of sildenafil on post-concussive symptoms and cognitive performance using two-sample t-test similarly as in the primary aim, but with the secondary endpoints of symptoms. On day 1 and 30 after injury we will then calculate the difference in CBF/CVR and each of the post-concussive symptom assessments and cognitive assessments after the single treatment of sildenafil. Also, we will assess the post-concussion correlations of CBF/CVR and cognitive performance by calculating the cross-sectional Pearson correlations of CBF/CVR with symptom inventory and neuropsychological CDEs collected at Day 1 and 30 after TBI. Correlations will be calculated separately and jointly at each time point, and for each of the subdomains of neuropsychological CDEs. Multiple comparisons will be adjusted by controlling the false discovery rate (FDR).

Our secondary analyses will consist of assessing the treatment effect of sildenafil therapy on brain biomarker levels using two-sample t testing, but with the secondary endpoints of symptoms. We will then calculate the difference in brain biomarker levels at the beginning of the sildenafil therapy and after the treatment period (Day 30 vs Day 1-3). Scatter plots including both arms will be generated based on the calculated differences and two linear regression models with changes in brain biomarkers as outcomes, and changes in symptoms as independent variables will be fit to assess the association between the recovery of the TBI-related markers. Potential confounders such as gender and treatment arm indicator will be adjusted in the model.

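### The lists of primary endpoints conflict, no primary visit, regimen comparison, testing order or success rule is given, and the one false-discovery-rate sentence has no stated scope

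*Combined protocol and SAP*

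**What the plan says.** Five places describe the primary set, and they do not agree.

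- **Section 10.1, Outcomes:** "The absolute changes in global and regional CBF/CVR to hypercapnia and improved symptoms and cognitive performance". All are primary, without ranking.
- **Protocol summary, Endpoint entry:** "The primary outcome measures will be global CVR to hypercapnia, reduced symptoms, improved cognition in concussed athletes". CBF and regional measures are absent.
- **Section 4.2.1:** "Hypothesis: Both single and multiple sildenafil therapy improves CBF/CVR, symptoms, and cognition in concussed boxers". CBF is back, and both regimens are in the hypothesis.
- **Section 10.1, Statistical analyses:** symptoms and cognition are tested "using two-sample t-test similarly as in the primary aim, but with the secondary endpoints of symptoms".
- **Section 10.1, Stopping rules:** "Even if we cannot reject the null hypothesis for the primary end point, we have multiple secondary endpoints". A single primary is implied.

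On timing, Section 4.2.1 has "At day 1-3 and 30 after injury, the CBF/CVR MR imaging procedures, the Rivermead Post Concussion Symptom Questionnaire, and neuropsychological assessments" at both follow-up points and ranks neither. Section 4.2.1.b lists five instruments (HVLT, SCAT5, SWLS, Rivermead, GOAT). None is named as the measure of symptoms or of cognition. The number of brain regions is not given.

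The analysis text has one sentence on multiple comparisons. It announces FDR control, comes straight after the correlation analyses, and gives no family, level or procedure. The power section states no significance level for the CVR comparison; its confidence level is attached to the correlation calculation.

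**The concern.** A primary endpoint should tell the reader, before the data are seen, which single result (or which combination) decides the trial. Here a significant difference in any listed outcome, any region, either visit or either regimen could be reported as a met primary endpoint, and nothing in the plan would contradict that report. The study is meant to supply the power calculation for a definitive trial (Section 10.1, Stopping rules), so an outcome picked from many because it was significant would also pass an inflated effect size to the next trial.

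**Working it through.** **1. The plan's own power figure.** Inputs from the power section: effect 0.86, SD of change 1.265 (its Table 1, correlation 0.2), 50 per arm. Two-sided 5% is my assumption.

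- Power ≈ Φ(0.86/1.265 × √(50/2) − 1.96) = Φ(3.40 − 1.96) = 92.5%, or 92.0% by the noncentral t. The plan states 80%, so that figure does not reproduce.
- At correlation 0.5 (SD 1.0) the signal term is 0.86 × 5 = 4.30 and power is 99%.

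The mismatch is a separate issue. I use 92% as the unadjusted baseline.

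**2. Chance of at least one false positive if treatment tests are not adjusted.** For m independent tests this is 1 − 0.95^m. For correlated tests I simulated equicorrelated normal statistics. The counts are assumptions, because the plan fixes none.

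| Assumed tests | Independent | r = 0.2 | r = 0.5 |
|---|---|---|---|
| 6: the summary's three outcomes, two visits | 1 − 0.95^6 = 26% | 25% | 21% |
| 12: global CBF, global CVR, Rivermead, HVLT, SCAT5, GOAT, two visits | 1 − 0.95^12 = 46% | 43% | 32% |
| 14: the same plus SWLS | 1 − 0.95^14 = 51% | 47% | 35% |
| 28: 14 in each regimen, tested separately | 1 − 0.95^28 = 76% | 72% | 57% |

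The two regimens are given to different athletes (Section 4.1), so the last row treats them as independent blocks: 1 − (1 − p)², with p from the 14-test row before rounding. Regional measures would raise every row that counts CBF or CVR.

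**3. CVR power if FDR does cover the treatment tests.** I simulated Benjamini-Hochberg at 5% over 14 independent tests with 50 per arm, using normal statistics. Each responding test is given the CVR effect; this is an assumption, since the plan gives an effect size for CVR only.

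| Tests responding, CVR included | Correlation 0.2 | Correlation 0.5 |
|---|---|---|
| 1 | 69% | 92% |
| 4 | 82% | 97% |
| 8 | 88% | 98% |

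A t reference lowers these by about 0 to 2 points (67%, 80% and 87% at correlation 0.2; 91% in the top cell at 0.5). For comparison, Bonferroni at 0.05/14 gives Φ(3.40 − 2.91) = 69% at correlation 0.2 and Φ(4.30 − 2.91) = 92% at 0.5 (66% and 90% by t).

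**4. Arm size.** Section 4.1 puts about 50 athletes in each regimen group. At 1:1 that is about 25 per arm within a regimen. Fifty per arm is therefore reached only if the regimens are pooled. At 25 per arm and correlation 0.2, one unadjusted CVR test has Φ(0.86/1.265 × √(25/2) − 1.96) = 67% power.

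**The case against.** - **The phrase that demotes symptoms may be a slip.** "but with the secondary endpoints of symptoms" occurs twice in the analysis text, the second time in the biomarker paragraph, where it makes no sense. It may be copied text. This stands: a reader might infer a deliberate reclassification, and the documents do not support that. The other lists still disagree, and CBF and CVR are never called secondary.
- **It is not a forced choice between uncontrolled error and lost power.** A reader might infer that it is. An all-must-succeed rule would keep the error rate and leave CVR's own power unchanged, although trial-level power would fall (three independent outcomes at 80% give 0.8³ = 51%). Under FDR, CVR keeps 80% or more if about four of 14 tests respond, and the trial's hypothesis is that all the outcomes improve. At correlation 0.5, which the plan also considers, power stays at about 90% or more. This stands, but the plan states no such rule and does not say which case applies.
- **The plan's power cannot be called unadjusted at 5%.** No alpha is given for it. This stands; the level used above is an assumption.
- **The test count is constructed.** Fair. SWLS measures life satisfaction and may not belong under symptoms or cognition, hence the 12-test row. Testing by regimen is also inferred. The smallest count, from the summary's own list, still gives 21-26%.
- **This is a single-site phase 2 study.** That lowers the stakes of a false claim but does not remove the need to say which result is primary.

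**Conclusion.** The concern holds in a limited form. The primary set is inconsistent across the summary, Section 4.2.1 and three parts of Section 10.1, and no visit, regimen comparison, order or success rule resolves it.

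If the treatment tests are unadjusted, the chance of a false-positive primary is 21-26% at the most modest count, 32-51% for 12-14 tests, and about 57-76% if 14 tests are run in each regimen. All of these assume two-sided 5% tests and the stated correlations.

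If FDR is meant to cover the treatment tests, it does not control the familywise rate once some outcomes truly respond. CVR power at correlation 0.2 then lies between about 69% (only CVR responds) and 88% (eight respond), against 92% unadjusted. The documents do not support the stronger inference that any adjustment must bring CVR power below the stated 80%: that happens only when few outcomes respond and the correlation is low.

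**What to change.** 1. Name one primary: the sildenafil-placebo difference in change in global CVR, with the visit and the reference visit for the change stated. Global CVR is in the summary's list and in Section 10.1, and CVR drives the plan's effect-size calculation.
2. State whether the regimens are pooled, which is the only reading that fits 50 per arm, or which one regimen is primary.
3. If the primary succeeds, test one named symptom instrument and then one named cognitive instrument in fixed sequence, each at the same two-sided 5%.
4. Put CBF, regional CVR, the remaining instruments, the other visit and the regimen-specific comparisons in one FDR family. Give its procedure and level, and say explicitly that it includes treatment comparisons.
5. Align the protocol summary, Section 4.2.1 and the Outcomes, Statistical analyses and Stopping rules text of Section 10.1, and correct both sentences that call symptoms secondary.
6. In the power section, state the alpha and the arm size that apply to the primary test.

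With pooled regimens the cost is wording and a restated power calculation, with no new data or visits. If one regimen is made primary, the arm is about 25 and the sample size has to be revisited. Symptoms and cognition become confirmatory only if CVR succeeds. Other single primaries would also be valid, provided one is named in advance.
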